Appendix III – continued

Question	Answer
What if a single non target lesion cannot be reviewed, for whatever reason; does this negate the overall assessment?	Sometimes the major contribution of a single non target lesion may be in the setting of CR having otherwise been achieved: failure to examine one non target in that setting will leave you unable to claim CR. It is also possible that the non target lesion has undergone such substantial progression that it would override the target disease and render patient PD. However, this is very unlikely, especially if the rest of the measurable disease is stable or responding
A patient has a 32% decrease in sum cycle 2, a 28% decrease cycle 4 and a 33% decrease cycle 6. Does confirmation of PR have to take place in sequential scans or is a case like this confirmed PR?	It is not infrequent that tumour shrinkage hovers around the 30% mark. In this case, most would consider PR to have been confirmed looking at this overall case. Had there been two or three non PR observations between the two time point PR responses, the most conservative approach would be to consider this case SD
In the setting of a breast cancer neoadjuvant study, would mammography not be used to assess lesions? Is CT preferred in this setting?	Neither CT nor mammography are optimal in this setting. MRI is the preferred modality to follow breast lesions in a neoadjuvant setting
A patient has a lesion measurable by clinical exam and by CT scan. Which should be followed?	CT scan. Always follow by imaging if that option exists since it can be reviewed and verified
A lesion which was solid at baseline has become necrotic in the centre. How should this be measured?	The longest diameter of the entire lesion should be followed. Eventually, necrotic lesions which are responding to treatment decrease in size. In reporting the results of trials, you may wish to report on this phenomenon if it is seen frequently since some agents (e.g. angiogenesis inhibitors) may produce this effect
If I am going to use MRI to follow disease, what is minimum size for measurability?	MRI may be substituted for contrast enhanced CT for some sites, but not lung. The minimum size for measurability is the same as for CT (10 mm) as long as the scans are performed with slice thickness of 5 mm and no gap. In the event the MRI is performed with thicker slices, the size of a measurable lesion at baseline should be two times the slice thickness. In the event there are inter slice gaps, this also needs to be considered in determining the size of measurable lesions at baseline
Can PET CT be used with RECIST?	At present, the low dose or attenuation correction CT portion of a combined PET CT is not always of optimal diagnostic CT quality for use with RECIST measurements. However, if your site has documented that the CT performed as part of a PET CT is of the same diagnostic quality as a diagnostic CT (with IV and oral contrast) then the PET CT can be used for RECIST measurements. Note, however, that the PET portion of the CT introduces additional data which may bias an investigator if it is not routinely or serially performed

REFERENCES


WHO 5.1.2 Unmeasurable Disease There are many forms of unmeasurable disease, and only a few are mentioned as examples: Lymphangitic pulmonary metastases. Skin involvement in breast cancer. Abdominal masses that can be palpated but not measured.
	
1.1. Baseline: Non-measurable Lesion Definitions Follow the definitions from RECIST 1.1. Non-target lesions will include:
 
 • Measurable lesions not selected as target lesions • All sites of non-measurable disease, such as neoplastic masses that are too small to measure because their longest uninterrupted diameter is < 10 mm (or < 2 times the axial slice thickness), ie. the longest per-pendicular diameter is >10 and < 15 mm. • Other types of lesions that are confidently felt to represent neoplastic tissue, but are difficult to measure in a reproducible manner. These include bone metastases, leptomeningeal metastases, malignant ascites, pleural or pericardial effusions, ascites, inflammatory breast disease, lymphangitis cutis/pulmonis, cystic lesions, ill-defined abdominal masses, skin lesions, etc. 	
Although irRC does not specifically define non-target lesions, irRC is derived from WHO criteria and indicates accordance with the same for the purposes of definitions of non-target lesions. Further clarifications in alignment with RECIST 1.1 are provided.

Not specified.
	
1.2 Baseline: Target and Non-Target Lymph Node Lesion Definitions Follow the definitions from RECIST 1.1.
	
No change in definition of target and non-target lymph nodes from RECIST 1.1.

Not specified.
	
1.3 Baseline: Non-Target Lesion Selection All lesions or sites of disease not recorded as target lesions should be recorded as non-target lesions at baseline. There is no limit to the number of non-target lesions that can be recorded at baseline.
	
In alignment with RECIST 1.1, all malignant lesions have to be selected at baseline. The excess of measurable lesions and all true non-measurable lesions will be selected as non-target lesions at baseline and followed at subsequent timepoints.

Not specified.
	
1.4 Baseline: Bone Lesions Follow the definitions from RECIST 1.1. Regardless of the imaging modality blastic bone lesions will not be selected as target lesions. Lytic or mixed lytic-blastic lesions with a measurable soft tissue component >10 mm can be selected as target lesions.
	
Bone lesions are to be handled the same as in RECIST 1.1.


Not specified.
	
1.5 Baseline: Brain Lesions detected on brain scans can be considered as both target or non-target lesions.
	
Brain lesions can be selected as target or non-target lesions at baseline, depending on the protocol definition, indication, and study design.

METHODS

Original irRC, Including WHO Criteria References	irRECIST Modifications and Clarifications	Rationale for Modification
Not specified.	
1.6 Baseline: Cystic and Necrotic Lesions as Target Lesions
 
Lesions that are partially cystic or necrotic can be selected as target lesions. The longest diameter of such a lesion will be added to the Total Measured Tumor Burden (TMTB) of all target lesions at baseline. If other lesions with a non-liquid/non-necrotic component are present, those should be preferred.
	RECIST 1.1 does not integrate viability of tumor tissue into the assessment, and that is carried over into irRECIST.
Not specified.	
1.7 Baseline: Lesions With Prior Local Treatment
 
During target lesion selection the radiologist will consider information on the anatomical sites of previous intervention (e.g. previous irradiation, RF-ablation, TACE, surgery, etc.). Lesions undergoing prior intervention will not be selected as target lesions unless there has been a demonstration of progress in the lesion.
	In order to minimize site vs. central discrepancy information about prior intervention needs to be available to both the investigators and independent reviewers.
Not specified.	
1.8 Baseline: No Disease at Baseline
 
If a patient has no measurable and no non-measurable disease at baseline the radiologist will assign 'No Disease' (irND) as the overall tumor assessment for any available follow-up timepoints unless new measurable lesions are identified and contribute to the TMTB.
	irND is a valid assessment in studies with adjuvant setting where the protocol and study design allow to include patients with no visible disease. This had not been addressed at all in any prior immune-response related criteria but needs to be included to also allow for these patients to be assessed accurately.
At each subsequent tumor assessment, the SPD of the index lesions and of new, measurable lesions ($\geq 5 \times 5$ mm; up to 5 new lesions per organ: 5 new cutaneous lesions and 10 visceral lesions) are added together to provide the total tumor burden: SPDindex lesions + SPDnew measured lesion	
2.0 Follow-up: Recording of Target and New Measurable Lesion Measurements
 
The longest diameters of non-nodal target and new non-nodal measurable lesions, and short axes of nodal target and new nodal measurable lesions will be recorded. Together they determine the Total Measured Tumor Burden (TMTB) at follow-up.
	In alignment with Nishino et al., 2013, unidimensional measurements are used. Measurements of all measured lesions (baseline-selected target lesions and new measurable lesions) are combined into TMTB at follow-up.
	
2.1 Follow-up: Definition of Measurable New Lesions
 
In order to be selected as new measurable lesions (≤ 2 lesions per organ, ≤ 5 lesions total, per timepoint), new lesions must meet criteria as defined for baseline target lesion selection and meet the same minimum size requirements of 10 mm in long diameter and minimum 15 mm in short axis for new measurable lymph nodes. New measurable lesions shall be prioritized according to size, and the largest lesions shall be selected as new measured lesions.
	Proposed selection of up to 5 new measurable lesions of at least 10 mm each versus 10 new measurable lesions as suggested in the irRC criteria is due to the following: 5 new measurable lesions add up at least 50 mm to the TMTB. Since PD is determined by at least a 20% increase in TMTB compared to nadir, this would mean that for irPD assessment the nadir TMTB had to be 25 cm, or 10 cm for 2 lesions in one organ, which is a significant tumor burden already for any cancer patient. That is why measuring up to 5 new lesions in total is sufficient and will not obstruct an irPD assessment. Measuring more than 5 new lesions is not needed. Larger lesions must be preferred as new measurable over smaller lesions, because there will be a greater impact of the TMTB %-increase by these larger lesions for irPD, to support a most conservative approach.

The adaptations from irRC and WHO criteria, as applicable in immunotherapy clinical studies, are documented in the "irRECIST Modifications and Clarifications" column in a comparative table format within our Blinded Independent Central Review (BICR) Charter.

The modifications we introduce represent adaptations of published criteria based on radiology practice and clinical trial experience, and they provide more objective and reproducible response assessments for investigators and for the central independent image review.

RESULTS

irRECIST criteria are based on irRC criteria adapted for unidimensional measurements, as outlined in Nishino et al., 2013. To further align the criteria with RECIST 1.1 we outline the approach for the assessment of baseline-selected non-target lesions and new non-measurable lesions, and discuss the impact of those lesions on the overall tumor response assessment.

Guidelines for the evaluation of patients with non-target disease only and patients in adjuvant setting is provided.

Original irRC, Including WHO Criteria References	irRECIST Modifications and Clarifications	Rationale for Modification
Non-index lesions at follow-up timepoints contribute to defining irCR (complete disappearance required).	
2.2 Follow-up: Non-Target Lesion Assessment
 
The RECIST 1.1 definitions for the assessment of non-target lesions apply.
 
The response of non-target lesions primarily contributes to the overall response assessments of irCR and irNon-CR/Non-PD (irNN). Non-target lesions do not affect irPR and irSD assessments. Only a massive and unequivocal worsening of non-target lesions alone, even without progress in the TMTB is indicative of irPD.
	Non-target lesions have a subordinate function. In the event that non-target lesions massively progress one cannot ignore such worsening and in these rare cases irPD based only on non-target lesions will be a valid assessment option.
New, non-measurable lesions at follow-up timepoints do not define progression, they only preclude irCR.	
2.3 Follow-up: New Non-Measurable Lesions Definition and Assessment
 
All new lesions not selected as new measurable lesions are considered new non-measurable lesions and are followed qualitatively. Only a massive and unequivocal progression of new non-measurable lesions leads to an overall assessment of irPD for the timepoint. Persisting new non-measurable lesions prevent irCR.
	When new non-measurable lesions substantially worsen in these rare cases irPD based only on new non-measurable lesions will be an assessment option.

irRC Overall Tumor Assessments
 
irCR, complete disappearance of all lesions (whether measurable or not, and no new lesions)
 
 Confirmation by a repeat, consecutive assessment no less than 4 weeks from the date first documented 
irPR, decrease in tumor burden $\geq 50\%$ relative to baseline
 
 Confirmed by a consecutive assessment at least 4 weeks after first documentation 
irSD, not meeting criteria for irCR or irPR, in absence of irPD
 
irPD, increase in tumor burden $\geq 25\%$ relative to nadir (minimum recorded tumor burden)
 
 Confirmation by a repeat, consecutive assessment no less than 4 weeks from the date first documented 	
2.4 irRC Overall Tumor Assessments
 
irCR, complete disappearance of all measurable and non-measurable lesions. Lymph nodes must decrease to $< 10\text{ mm}$ in short axis. Confirmation of response is not mandatory.
 
irPR, decrease of $\geq 30\%$ in TMTB relative to baseline, non-target lesions are irNN, and no unequivocal progression of new non-measurable lesions.
 
irSD, failure to meet criteria for irCR or irPR in the absence of irPD.
 
irNN, no target disease was identified at baseline and at follow-up the patient fails to meet criteria for irCR or irPD.
 
irPD, minimum 20% increase and minimum 5 mm absolute increase in TMTB compared to nadir, or irPD for non-target or new non-measurable lesions. Confirmation of progression is recommended minimum 4 weeks after the first irPD assessment.
 
irNE, used in exceptional cases where insufficient data exists.
 
irND, in adjuvant setting when no disease is detected.
	
The irRECIST overall tumor assessment is based on TMTB of measured target and new lesions, non-target lesion assessment and new non-measurable lesions.
 
The thresholds for irPR and irPD assessment are aligned with RECIST 1.1, and confirmation of response is not required.
 
An irPD confirmation scan may be recommended for patients with a minimal TMTB %-increase over 20% and especially during the flare time-window of the first 12 weeks of treatment, depending on the compound efficacy expectations, to account for expected delayed response.

CONCLUSIONS

irRECIST criteria as outlined here introduce the needed clarifications and adjustments to irRC criteria and Nishino et al., 2013 publication to allow for treatment evaluations that better meet both investigators' and patients' needs and with that better reflect sponsors' demands for more reliable and reproducible study data in targeted immunotherapy in oncology studies. The main adaptation of the existing immune-response criteria lies in the assessment of all detected lesions. Unequivocal and substantial increase of non-target and new non-measurable lesions prevents irCR and may also lead to irPD. Reduction of the tumor burden in patients in an adjuvant setting may lead to irPR and such patients may therefore be enrolled in studies with response endpoints.

Clinical relevance of these adaptations needs to be confirmed.

SUMMARY AND ADDITIONAL GUIDANCE

1. TMTB: Baseline-selected target lesions and new measurable lesions should NOT be assessed separately. Measurements of those lesions should be combined into the Total Measured Tumor Burden (TMTB), and one combined assessment provided.
2. New Measurable Lesions: According to irRC a measurable new lesion has to be at least 5 mm x 5 mm to be selected as an index lesion. For bidimensional measurements this threshold was acceptable. In irRECIST, criteria for unidimensional lesion measurement apply to both target and new measurable lesions: a minimum 10 mm in the longest diameter for non-nodal lesions, and a minimum 15 mm in short axis for lymph nodes. Smaller lesions contribute to the non-target or new non-measurable tumor burden, but do not get measured.
3. irPR if no Target Lesions: If new measurable lesions appear in patients with no target lesions at baseline, irPD will be assessed. That irPD timepoint will be considered a new baseline, and all subsequent timepoints will be compared to it for response assessment. irPR is possible if the TMTB of new measurable lesions decreases by $\geq 30\%$ compared to the first irPD documentation.
4. irPR in Adjuvant Studies: irRECIST can be used in the adjuvant setting, in patients with no visible disease on CT/MRI scans. The appearance of new measurable lesion(s) automatically leads to an increase in TMTB by 100% and leads to irPD. These patients can achieve a response if the TMTB decreases at follow-up, as a sign of delayed response.
5. Non-Target Lesions: In alignment with RECIST 1.1, baseline selected non-target lesions can never convert to measurable lesions, not even if they increase in size at subsequent timepoints and become measurable. Only true new lesions can be measured and contribute to the TMTB.
6. Example: A patient has multiple lung metastases, all smaller than 10 mm and selected as non-target lesions at baseline. If, at a subsequent timepoint some of these non-target lesions increase and become > 10 mm, and one new lesion > 10 mm appears, only the new measurable lesion will contribute to the TMTB, and not the baseline selected non-target lesion that increased in size. Otherwise such an increase would make persisting non-target lesions switch into the new measurable lesion category which would be inaccurate, as the lesion existed at baseline.
7. irPD Based on Non-Target Lesions: Unlike irRC that neglect non-target lesions for the assessment of irPD, in irRECIST a substantial and unequivocal increase of non-target lesions is indicative of progression.
8. irPD Based on New Non-Measurable Lesions: According to irRC, a patient with multiple new lesions of 9 mm would be considered non-PD, whereas a patient with just one new lesion of 10 mm may be assessed as irPD if the TMTB of such a patient increases $\geq 20\%$ compared to nadir. According to irRECIST, the reviewer may assign irPD for the patient with multiple new lesions of 9 mm if they are considered to be a sign of unequivocal, massive worsening (see 2.3)
9. irPD Confirmation: Progression confirmation no less than 4 weeks after the initial irPD assessment is recommended especially in case of marginal disease growth and if the first irPD assessment is within the compound-specific tumor flare window.

REFERENCES

- 1) JD Wolchok, A Hoos, O Bohnsack, et.al., Guidelines for the Evaluation of Immune Therapy Activity in Solid Tumors: Immune-Related Response Criteria, *Clin Cancer Res* 2009;15[23] December 1, 2009
- 2) Nishino M et al. Developing a common language for tumor response to immunotherapy: immune-related response criteria using unidimensional measurements. *Clin Cancer Res.* 2013 Jul 15;19[14]:3936-43

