3.1.3 Efficacy Parameters

Efficacy will be evaluated based on assessments of tumor response and progression using the standardized RECIST, Version 1.1 ([Eisenhauer 2009](#); [Appendix 7](#)).

Efficacy endpoints will include:

- Overall response rate (ORR)
- Disease control rate (DCR)
- Duration of response (DOR)
- Progression-free survival (PFS)
- Overall survival (OS)

Efficacy endpoints will include:

- irORR (irCR + irPR)
- irDCR (irCR + irPR + irSD)
- irDOR
- irPFS

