4.2.1 Determination of Response at Each Timepoint (RECIST)

The tumor response at each timepoint will be determined. [Table 4-3](#) provides a summary of the overall response status calculation at each timepoint.

Table 4-3. Timepoint Response (RECIST)

Target Lesions	Nontarget Lesions	New Lesions	Overall Response
CR	CR	No	CR
CR	Non-CR/non-PD	No	PR
CR	Not evaluated	No	PR
PR	Non-PD or not all evaluated	No	PR
SD	Non-PD or not all evaluated	No	SD
Not all evaluated	Non-PD	No	NE
PD	Any	Yes or No	PD
Any	PD	Yes or No	PD
Any	Any	Yes	PD

Abbreviations: CR = complete response; PD = progressive disease; PR = partial response; SD = stable disease; NE = nonevaluable.

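### Appendix 8 contradicts itself on irPR: item 2.4 requires non-target disease to persist, item 2.2 says it has no bearing, so a deeper response can be scored irSD and drop out of irORR and irDOR

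*Protocol*

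**What the plan says.** Section 3.1.3 lists "irORR (irCR + irPR") and irDOR among the efficacy endpoints. Section 4.2.3 makes the irRECIST adaptations in Appendix 8 the operative rules. Section 5.4.4 has ORR and DCR evaluated by irRECIST as well as by RECIST 1.1, and names ORR by RECIST as primary.

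Appendix 8 then speaks to irPR in two places.

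- Item 2.4 (overall tumor assessments) asks for a fall of at least 30% in total measured tumor burden (TMTB) from baseline, and adds "non-target lesions are irNN, and no unequivocal progression of new non-measurable lesions". The category below it is residual: "irSD, failure to meet criteria for irCR or irPR in the absence of irPD".
- Item 2.2 (non-target lesions at follow-up) says "The RECIST 1.1 definitions for the assessment of non-target lesions apply", then "The response of non-target lesions primarily contributes to the overall response assessments of irCR and irNon-CR/Non-PD (irNN"), and then "Non-target lesions do not affect irPR and irSD assessments". Only massive, unequivocal worsening of non-target disease counts, and it counts towards irPD.

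For RECIST itself, Table 4-3 in Section 4.2.1 gives PR when the target lesions are PR, there are no new lesions, and the non-target lesions are "Non-PD or not all evaluated".

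**The concern.** Item 2.4 makes irPR depend on non-target status; item 2.2 says that it does not. Item 2.4 looks like the definition that a site or programmer would code, because it lists the categories one by one. Coded as written, it ranks responses in the wrong order: a subject whose non-target lesions have cleared can be placed below one whose non-target lesions remain.

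At stake are irORR and irDOR. Two assessors who follow different items of the same appendix could classify the same scan differently. A subject could also be PR by RECIST and irSD by irRECIST on that scan, although Section 4.2.3 adopts irRECIST because standard RECIST may misjudge responses to immunotherapy.

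**Working it through.** **Step 1. What irNN means for a lesion group.** Item 2.2 expands irNN as Non-CR/Non-PD and imports the RECIST 1.1 non-target definitions. Table 4-2 defines Non-CR/Non-PD as persistence of at least one non-target lesion and/or a tumor marker still above normal. Non-target lesions that have all gone, with any marker normal, are CR, not Non-CR/Non-PD. Table 4-3 keeps the two ideas apart: one row uses Non-CR/non-PD, others use the wider non-PD.

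**Step 2. Run the rules on one example.** Take a TMTB fall of 45%, target lesions still visible, no new lesions.

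| Non-target lesions | Item 2.4 as written | Item 2.2 | Table 4-3 (RECIST) |
|---|---|---|---|
| Persist, not progressing | irPR | irPR | PR |
| All disappeared, marker normal | irSD | irPR | PR |
| Not all evaluated | not settled (irPR, irSD or irNE) | irPR | PR |
| None at baseline | irPR (condition is vacuous) | irPR | PR |

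The second row carries the contradiction. The subject is not irCR, because target lesions remain. The subject is not irPR under item 2.4, because non-target status is CR rather than irNN. Nothing has progressed, so the subject is not irPD. The residual category, irSD, is all that is left.

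**Step 3. Who would actually be lost.** Appendix 8 does not require confirmation of response, and Section 5.4.4 counts subjects who achieve a response. Scans fall at Weeks 7, 13 and 19, then every 12 weeks (Section 4.1.19). A subject with a fall of at least 30% at one scan while non-target lesions persist is irPR there, and stays in irORR if those lesions clear later. A subject who later reaches irCR is also counted, though with a later start for irDOR. Those lost from both summaries never show the 30% fall together with persisting non-target disease and never reach irCR.

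**Step 4. What cannot move.**

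- Futility (Section 5.5) uses irDCR = irCR + irPR + irSD. Moving k subjects from irPR to irSD gives irCR + (irPR − k) + (irSD + k), which is the same total.
- The primary endpoint is ORR by RECIST, governed by Table 4-3.
- The sample size rests on projected response rates of 40% and 18%, one-sided alpha 0.10 and 80% power (Section 5.1). With unpooled variance, n = (1.2816 + 0.8416)² × (0.18 × 0.82 + 0.40 × 0.60) / 0.22² = 4.508 × 0.3876 / 0.0484 = 36.1, rounded up to the 37 per arm in the synopsis. The irPR rule is not an input.

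**Step 5. Scale.** One misscored subject in a full arm changes irORR by 1/37 = 2.7 percentage points. The documents give no figure for how many subjects that would be.

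**The case against.** The best defence is that the appendix already settles the matter. Item 2.2 is the item that sets the role of non-target lesions, and it is explicit. The rationale beside item 2.4 says that the irPR threshold follows RECIST 1.1, and Section 4.2.3 takes RECIST 1.1 as its base. On that reading, irNN in the irPR clause simply means not progressing.

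The literal reading is also not the only one, because item 2.4 uses the same abbreviation for a subject-level category: "irNN, no target disease was identified at baseline and at follow-up the patient fails to meet criteria for irCR or irPD". Every subject here must have measurable disease at entry (inclusion criterion 4), so under that meaning even a subject with persisting non-target lesions could not be irPR. Finally, the appendix reproduces a published poster, and the programming of irPR may be settled in an SAP that is not at hand.

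Much of this stands. Item 2.2 supports the sensible reading, so misscoring is possible, not certain. But the protocol does not say that item 2.2 overrides item 2.4, and a second meaning of irNN within item 2.4 adds to the ambiguity. Reproducing a poster does not make its wording harmless once Section 4.2.3 adopts it as a rule.

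**Conclusion.** The contradiction is real and lies in the stated rules. Its reach is narrow: irORR and irDOR, and only if item 2.4 is followed over item 2.2 for subjects as described in Step 3. The size of the effect cannot be derived from the documents and is probably small.

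Four stronger readings are tempting and are not supported.

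- *Such responders are certainly scored irSD.* Item 2.2 gives the opposite answer, so the outcome depends on which item is applied.
- *Subjects without non-target lesions at baseline also fail.* A condition on lesions that do not exist is met vacuously.
- *irORR falls by a calculable amount.* Multiplying the planned 18% and 40% by an assumed share of responders, say 10% to 30%, gives losses of 1.8 to 5.4 and 4.0 to 12.0 points. Nothing in the documents supports that share, the rates were planned for ORR by RECIST, and the calculation ignores subjects already irPR at an earlier scan.
- *A planned comparison between the two criteria is biased.* Section 5.4.4 has the endpoints evaluated by both; it states no formal contrast between them.

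Treatment decisions are untouched as well, because continuation and crossover turn on confirmed progression (Section 3.11). This is a minor point, worth correcting because the correction is so cheap.

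**What to change.** Add one sentence to Section 4.2.3, for example: *For irPR in this study, non-target lesions must not be irPD; they may be CR, Non-CR/Non-PD, not all evaluated, or absent at baseline. This replaces the irNN condition in the irPR definition of Appendix 8, item 2.4.* The requirement of no unequivocal progression in new non-measurable lesions stays as it is. Program irORR and irDOR on that rule.

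This brings item 2.4 into line with item 2.2 and Table 4-3. It needs no new data, because non-target status is already assessed at each tumor evaluation, and it leaves the primary analysis, the futility boundaries and the sample size unchanged. It should be in place before irORR is programmed.
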